We propose to perform a prospective, randomized, double-blind placebo controlled trial. Patients will be included if they are: 1) receiving outpatient hemodialysis at the James J. Peters VAMC, 2) receiving IV vitamin D therapy according to National Kidney Foundation guidelines, 3) between the ages of 45-89 years, 4) a veteran outpatient or stable community living center patient, and 5) able to ambulate independently or with an assistive device for at least 20 feet. Exclusion criteria include: 1) 25-OH vitamin D level \geq 25 ng/ml, 2) hypercalcemia, 3) active malignancy within 6 months, 4) receiving intravenous antibiotics for infection, 5) history of dementia, 6) hemoglobin $<$ 8.5g, 7) history of conditions that interfere with postural instability (e.g. cerebellar disease, vestibular disease or any others that may present), and 8) poor compliance with dialysis treatments (history of skipping \geq 2 treatments per month for $>$ 2 months). A 25-OH vitamin D level of $<$ 25 ng/ml level was chosen based on previous studies that have shown that patients have the greatest improvement in muscle strength when levels below this threshold are increased. Patients will first be identified based on the inclusion criteria, then informed about the study and consented. Those who meet the exclusion criteria will be randomized to treatment or placebo. Enrolled participants will be randomized 2:1 to receive vitamin D (n=20) or placebo (n=10) for 6 months. All participants will be tested twice over two weeks to establish baseline values. Following baseline testing, the treatment group will receive 50,000 IU (standard replacement therapy) of oral cholecalciferol or placebo. The initial dose of cholecalciferol will be 50,000 IU weekly for 6 weeks. Vitamin D levels will then be measured. Participants who still have Vitamin D insufficiency (\leq 35 ng/ml) will remain on 50,000 IU of cholecalciferol for another 6 weeks, at which point Vitamin D levels will be measured again. Participants who reach 25-OH levels $>$ 35 ng/ml will have their dosing regimen lessened to 10,000 IU weekly (maintenance dose) for the remainder of the 6 months. Participants receiving placebo will start taking the placebo maintenance dose after the first 6 weeks. For safety monitoring, 25(OH) vitamin D₃ levels will also be re-measured at monthly intervals and followed by an independent medical monitor. In patients who have serum vitamin D levels \geq 60

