ng/ml, the frequency of administration will be reduced to once a month. The participants will receive supplementation for a total of 6 months. At this time, vitamin D levels will be reassessed and participants will undergo follow-up functional assessments, and cognitive and immune testing. Subjects will be recruited from the outpatient hemodialysis (HD) unit which is located on the fourth floor of the James J. Peters VAMC.

Primary Outcomes (tested at Baseline, 3 months and 6 months):

- 1) Neuromuscular functional performance using the 50ft timed walk, the TUG, a timed stair climb, and the Chair Raise test, (48)
- 2) Postural stability using a Sway meter (NeuroCom International, Inc., Clackamas, OR) that measures displacement of the body at the level of the waist in 30 second periods (49) and the Functional Reach test.
- 3) Muscle hand grip strength using the Harpenden Hand Grip dynamometer (50) and hip flexor and knee extensor strength using a Push-Pull Muscle Strength dynamometer.

Secondary Outcomes:

- 1) Cognitive function (tested at Baseline, 3 and 6 months):
 - a) Mental Status: Mini-Mental Status Exam (MMSE) (51) and Short Blessed Test (SBT) (52);
 - b) Memory: California Verbal Learning Test – II (CVLT-II) (53);
 - c) Language: Category Fluency and Controlled Oral Word Association Test (COWAT) (54);
 - d) Attention and Processing Speed: Trails A (55), Digit Span (56), Symbol Digit Modality Test (SDMT) (57), and Stroop Color and Word (58)
 - e) Executive Function: Trails B (55) and Stroop Color-Word (58).
- 2) Self-assessment of Physical Fxn and Health (tested at Baseline, 3 months and 6 months):
 - a) Physical Activity Scale for Persons with Physical Disabilities (PASIPD) (59)
 - b) NIH PROMIS (v1.0 Item Banks): Global Health Physical Function, Pain, Fatigue, Sleep, Emotional Distress (60)
 - c) Beck Depression Inventory (BDI)
- 3) Immunology (tested at Baseline, 6 months)
 - a) Serum cytokines

This study will be performed over two years.

TABLE 1. Study Flow Sheet	BL 1	BL 2	Month 1	6 weeks	Month 2	Month 3	Month 4	Month 5	Month 6
Week:	0	0 ₂	4	6	8	12	16	20	24
Physical Function Assessment 50ft walk, TUG, stair climb, Chair Raise, Functional Reach, Sway, Hand Grip, Hip & Knee Strength		X				X			X
Self - Assessment PASIPD & NIH PROMIS (short forms): Physical Fxn, Pain, Fatigue, Global Health, Sleep, Emotional Distress, BDI		X				X			X
Cognitive Impairment Tests									

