Immune Function Analysis Primary analysis will compare study subjects who had a 25-OH level > 35 ng/ml to study subjects who remained at a level ≤ 35 ng/ml (Vitamin D deficient/insufficient). Potential confounders that will be examined include age, 25-OH Vitamin D level at Baseline, time on HD, sex, and ethnicity. Variables that differ significantly between treatment arms at an alpha of 0.01 and are significantly related to the immune outcomes at an alpha of 0.05 will be included in multivariable analysis. If potential confounders meet the criteria for inclusion, the multivariable analysis will be the primary analysis.

a. Basic Information (Even if described under “Procedures”, list the information requested below where pertinent.)

1. What procedures will be used (i.e. biopsy, surgical operation, interview, experimental diet, infusion, drug administration, etc.) and with what frequency?

All participants will have their serum Vitamin D levels tested twice over two weeks to establish baseline values. Following baseline testing, the treatment group will receive 50,000 IU (standard replacement therapy) of oral cholecalciferol or placebo. The initial dose of cholecalciferol will be 50,000 IU weekly for 6 weeks. Vitamin D levels will then be measured. Participants who still have Vitamin D insufficiency (≤ 35 ng/ml) will remain on 50,000 IU of cholecalciferol for another 6 weeks, at which point Vitamin D levels will be measured again. Participants who reach 25-OH levels > 35 ng/ml will have their dosing regimen lessened to 10,000 IU weekly (maintenance dose) for the remainder of the 6 months. Participants receiving placebo will start taking the placebo maintenance dose after the first 6 weeks. 25(OH) vitamin D₃ levels will also be re-measured at monthly intervals and followed by an independent medical monitor. In patients who have serum vitamin D levels ≥ 60 ng/ml, the frequency of administration will be reduced to once a month. The participants will receive supplementation for a total of 6 months.

The following outcomes will be tested at **Baseline, 3 months and 6 months**:

Physical Functional assessments:

- 1) Neuromuscular functional performance using the 50ft timed walk, TUG test, a timed stair climb, and Chair Raise test, (48)
- 2) Postural stability using a Sway meter (NeuroCom International, Inc., Clackamas, OR) that measures displacement of the body at the level of the waist in 30 second periods (49) and the Functional Reach Test.

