The main risk in this study is vitamin D toxicity. Vitamin D toxicity usually manifest first with hypercalcemia, which will be monitored by routine monthly dialysis lab tests. Moderate to severe hypercalcemia can result in symptoms of increased urinary frequency, thirst, nausea, vomiting, confusion, decreased appetite, and muscle weakness. Hypercalcemia will be first managed by adjustment of IV vitamin D (administered according to National Kidney Foundation Guidelines (NKF)) which is titrated by the patient's nephrologist and much more likely to be responsible for hypercalcemia versus oral 25-OH vitamin D. If these measures do not correct hypercalcemia, oral vitamin D supplementation will be discontinued. Efforts to correct hypercalcemia will occur as soon as the calcium levels are rise above the upper limits of normal (10.5 mg/dl) which is usually not associated with the above listed clinical symptoms.

The physical function and health questionnaires are non-invasive. The risks associated with venipuncture include: pain, bruising, swelling, and/or infection at the site of the needle puncture; and rarely fainting may also occur. There is the potential for the subject to experience some mild frustration during the cognitive impairment studies. A trained psychologist will be administering the tests.

2. Include estimates of degree of risk with documentation from recent medical literature.

We do not anticipate any patients to develop vitamin D toxicity due to our careful selection of dosing regimen that was based on previous studies. Vitamin D levels will be monitored each month along with monthly dialysis blood tests that are routinely performed on HD patients. If vitamin D levels rise above 60 ng/ml, (conservative cut off point since most reports of toxicity occur > 80 ng/ml) the frequency of

administering vitamin D will be reduced to once a month which is considered routine maintenance dosing to prevent vitamin D deficiency.

Physical function and health questionnaires, venipuncture, and cognitive assessments present minimal risk.

3. What monitoring or other safety precautions will be taken?

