To protect against the any possible side effects of vitamin D supplementation toxicity, subjects' 25-OH vitamin D levels will be monitored. If a subject reaches 25-OH levels ≥ 60 ng/mL, the dose will be immediately lowered. As the PI, I will remain blinded and review monthly calcium levels to monitor for evidence of hypercalcemia. When hypercalcemia is identified, the patient's primary nephrologist will be notified so that appropriate adjustments can be made to correct hypercalcemia. The primary nephrologist's first adjustment will be to decrease the dose of IV vitamin D according NKF guidelines.

To protect against the risk of possible side effects of the blood draw, the study personnel will be trained in phlebotomy. To remove as much frustration as possible during the cognitive tests, a trained psychologist will be administering the tests.

c. Possible Benefits

Describe possible benefits from this study and state whether these benefits will be to experimental subject, to others, or both.

The benefits of vitamin D supplementation could possibly include improved muscular, cognitive, and immune function. Improvement of muscular function may allow for more patient independence on IADLs. Interventions that improve cognitive function may also lead to a healthier, more compliant HD patient. These benefits will be to experimental participants. This research also has the potential to benefit others in the future.

D) PREVIOUS WORK DONE BY YOU OR YOUR COLLABORATORS ON THIS OR RELATED PROJECTS, LISTING PUBLICATIONS.

Prevalence of Mild Cognitive Impairment in HD patients: We have collected data from 40 patients undergoing HD at the James J. Peters VAMC to determine if mild cognitive impairment exists in a healthy population with normal MMSE scores (>24) and no clinical history of stroke. Subjects were all male with a mean age of 64 ± 10 y (range: 45-82y), an education level of 13 ± 2 y, and 80% were non-Caucasian. All subjects underwent a comprehensive neurocognitive battery which captured the domains of memory, language, attention & processing speed, and executive function.

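### The cut to monthly dosing at 60 ng/ml or above is visible in the unit and in practice marks vitamin D, in a trial described as double-blind; dummy weekly doses would hide it

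*Combined protocol and SAP*

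**What the plan says.** Section C, Research Design and Methods, states: "We propose to perform a prospective, randomized, double-blind placebo controlled trial". Allocation is 2:1, with 20 participants on vitamin D and 10 on placebo, and entry requires a 25-OH vitamin D level below 25 ng/ml.

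The same section sets the dosing rules, and items a.1 and a.2 of section C repeat them:

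- Vitamin D participants start on 50,000 IU weekly for six weeks.
- At week 6, those at or below 35 ng/ml "will remain on 50,000 IU of cholecalciferol for another 6 weeks, at which point Vitamin D levels will be measured again".
- Those above 35 ng/ml "will have their dosing regimen lessened to 10,000 IU weekly (maintenance dose) for the remainder of the 6 months".
- For placebo the schedule is fixed: "Participants receiving placebo will start taking the placebo maintenance dose after the first 6 weeks".
- For high levels: "In patients who have serum vitamin D levels ≥ 60 ng/ml, the frequency of administration will be reduced to once a month". Item b.2 gives the same reduction for levels above 60 ng/ml, the frequency of "administering vitamin D will be reduced to once a month which is considered routine maintenance dosing". Item b.3 says: "If a subject reaches 25-OH levels ≥ 60 ng/mL, the dose will be immediately lowered".

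Section B (Dosing of 25-OH vitamin D in HD Patients) has research staff give the supplement in the unit. An independent medical monitor follows the monthly levels, and item b.3 keeps the principal investigator blinded. Under item a.2 a physical therapist runs the physical tests and a research assistant does the self-report surveys. No dummy dose between monthly doses is described.

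**The concern.** Blinding can fail through the schedule even when the products look identical. Someone who has received a dose every week and then receives one a month can see the difference, and so can the person giving it. If only one arm can realistically have that change, it reveals the allocation to anyone who knows the rule.

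Most primary outcomes depend on effort: the 50 ft walk, Timed Up and Go, stair climb, chair raise, grip, and hip and knee strength. PASIPD, PROMIS and the BDI are self-reported. Knowing the arm could shift any of these. Postural sway, the endpoint named in H1, is measured by instrument, and cytokines are a laboratory measure, so both are less exposed. The pilot is meant to inform a pivotal trial, so what is at stake is mainly the trustworthiness of its effect estimates.

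**Working it through.** The plan gives no figure on this point to reproduce. The check compares the rules by arm and asks what each visible event reveals.

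**1. Can placebo participants reach 60 ng/ml?** Inputs: entry level below 25 ng/ml (Research Design and Methods); 39 preliminary patients with mean 12.86, SD 8.03 and maximum 37.67 ng/ml (section D).

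- Distance from the highest observed value: 60 − 37.67 = 22.33 ng/ml.
- Distance from the mean: (60 − 12.86)/8.03 = 5.87 SD.
- None of 39 reached 60. One-sided 95% upper bound: 1 − 0.05^(1/39) = 7.4%, or 10 × 0.074 = 0.74 of the 10 placebo participants. The entry limit makes the real figure lower still.

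These numbers show that placebo will almost never trigger the rule. They say nothing about how often vitamin D will.

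**2. How visible is the cut, and when can it come?** Table 1 schedules levels at weeks 4, 6, 8, 12, 16, 20 and 24.

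- Cut at week 4: 24 − 4 = 20 weekly slots remain, 5 become monthly doses, and 15 are lost.
- Cut at week 8: 24 − 8 = 16 slots remain, 4 become monthly doses, and 12 are lost.

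A cut can therefore precede both the week-12 and week-24 assessments.

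**3. Week 6, rules side by side.** Every placebo participant moves to placebo maintenance. Vitamin D participants above 35 ng/ml move to 10,000 IU weekly, so the step-down happens in both arms. Vitamin D participants at or below 35 ng/ml stay on 50,000 IU weekly, and no placebo participant does. Anyone still on loading after week 6 is thus on vitamin D. Both doses are weekly, so the schedule itself shows nothing; the difference is seen only if the strengths can be told apart. The documents do not describe their appearance.

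**4. What would such events reveal?** Let x be the number of the 20 vitamin D participants with an event that occurs only on vitamin D and is recognised as such. The documents do not give x, so the whole range is shown.

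- Chance of vitamin D given no event: (20 − x)/(30 − x).
- Best-guess accuracy over all 30: [x + max(20 − x, 10)]/30.

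| x (assumed) | Identified with certainty | Chance of vitamin D if no event | Best-guess accuracy |
|---|---|---|---|
| 0 | 0 | 67% | 67% |
| 1 | 1 | 66% | 67% |
| 2 | 2 | 64% | 67% |
| 5 | 5 | 60% | 67% |
| 10 | 10 | 50% | 67% |
| 15 | 15 | 33% | 83% |
| 20 | 20 | 0% | 100% |

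Up to x = 10, the effect is certainty about a subset, with no gain in overall guessing. Beyond that, overall guessing improves too.

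**5. Size of bias.** This would need x and the change in outcome caused by knowing the arm. The documents give neither, so no figure is offered.

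**The case against.** The strongest reply is that the monthly cut may hardly ever happen. Above 35 ng/ml the weekly dose falls from 50,000 to 10,000 IU. A level of 60 then needs an early overshoot on loading, a further rise on the lower dose, or a rise of at least 60 − 35 = 25 ng/ml in someone kept on loading. One study described in section B gave 20,000 IU weekly for nine months, twice the planned maintenance dose, then monthly; only 57% exceeded 30 ng/ml. The regimen differs, so this is a rough guide, but the number cut to monthly dosing could be close to zero. This stands, and it limits the severity.

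Seeing a change is also different from decoding it. These patients already have intravenous vitamin D and phosphate binders adjusted on monthly laboratory results, so another adjustment may mean little to them. The argument is stronger for dosing staff, but the documents do not say that dosing staff collect outcomes; equally, they do not say that the roles are separate. The monitor, the blinded principal investigator and the physical therapist are real safeguards, although none hides a schedule change from the participant or the person giving the dose.

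A reader might go further in four ways that the documents do not support:

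- *The monthly rule is written only for vitamin D.* It is worded for all patients; only its effect is specific to one arm.
- *The trial is in effect open-label.* That needs a large x, and x is unknown.
- *The two strengths look different.* Silence about appearance is not evidence of a mismatch.
- *A given number of spurious responders will result.* That needs an assumed gain per unmasked participant, for which the documents offer no basis.

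**Conclusion.** The concern holds, as a minor point. The cut to monthly dosing is visible and in practice can arise almost only on vitamin D, and nothing in the plan hides it from participants or dosing staff. The missing counterpart to the week-6 extension is a lesser gap, conditional on the strengths being distinguishable. Identification also requires knowing the rule.

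The conclusion rests on the preliminary patients being a fair guide to levels without study supplementation, and on no dummy doses being planned, since none is described. The number affected is unknown and may be small, so neither the direction nor the size of any bias in the effort-dependent and self-reported outcomes can be stated.

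**What to change.** When a participant's vitamin D goes to monthly, keep giving a matching oral dose in the unit every week, with dummies in the off-weeks, so that the schedule looks the same in both arms. Have the pharmacy or the independent monitor direct the change. Use matching products for 50,000 IU, 10,000 IU and placebo; this also closes the week-6 gap without sham extensions. One sentence stating that whoever gives doses does not collect outcomes would be a useful addition.

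The cost is a short protocol clarification, matching products, a small pharmacy or monitor task, and at most about 15 dummies per affected participant (cut at week 4: 20 weekly slots less 5 monthly doses). Patients already attend dialysis three times a week, so no visits are added. Vitamin D dose, the 60 ng/ml safety rule and the sample size are unchanged.

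### The dose-reduction rules at >35 and ≥60 ng/ml contradict each other, and on a literal reading the safety cut can leave a higher monthly dose than the routine step-down

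*Combined protocol and SAP*

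**What the plan says.** The stepped regimen appears three times in section C: under Research Design and Methods, and under Basic Information, items 1 and 2. It begins: "The initial dose of cholecalciferol will be 50,000 IU weekly for 6 weeks". Participants at or below 35 ng/ml at that point "will remain on 50,000 IU of cholecalciferol for another 6 weeks, at which point Vitamin D levels will be measured again". Those above 35 ng/ml "will have their dosing regimen lessened to 10,000 IU weekly (maintenance dose) for the remainder of the 6 months". This rule states both the amount and the frequency.

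The safety rule follows in the same paragraphs: "In patients who have serum vitamin D levels ≥ 60 ng/ml, the frequency of administration will be reduced to once a month". It states a frequency and no amount.

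Three other places describe the action at about 60 ng/ml, each differently:

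- List Possible RISKS, item 2, says that the frequency of "administering vitamin D will be reduced to once a month which is considered routine maintenance dosing to prevent vitamin D deficiency". Section C, however, attaches the maintenance label to 10,000 IU weekly.
- List Possible RISKS, item 3, speaks of dose and not of frequency: "If a subject reaches 25-OH levels ≥ 60 ng/mL, the dose will be immediately lowered".
- Section B, Dosing of 25-OH vitamin D in HD Patients, proposes 50,000 units every week with the dose adjusted above 60 ng/mL. It mentions no 10,000 IU step.

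The boundary also varies between ≥60 and above 60. No section gives the IU per monthly administration or says which rule takes precedence.

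**The concern.** The two thresholds are nested: a level of 60 or more is always above 35 as well. One rule changes the amount and keeps weekly dosing. The other changes the frequency and is silent on the amount. Staff who have a result of 60 or more for a participant on 50,000 IU weekly could apply either rule alone or both together, and each choice follows some sentence of the protocol.

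On the most literal choice, where only the frequency changes, the participant with the higher level ends up on more vitamin D per month than one stepped down routinely just above 35.

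The protocol names vitamin D toxicity as its main risk (List Possible RISKS, item 1), and safely raising 25-OH levels with this regimen is one of the pilot's goals (Specific Aims). A safety rule that can be carried out in three ways in this group of 20 treated participants weakens the evidence on that goal.

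**Working it through.** The documents state no monthly dose total, so there is no figure of the plan's own to reproduce. The check is dose arithmetic on the stated regimens.

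**Inputs** (section C, Research Design and Methods; repeated in Basic Information, items 1 and 2)

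- Loading: 50,000 IU weekly.
- Routine step-down above 35 ng/ml: 10,000 IU weekly.
- Safety cut at ≥60 ng/ml: once a month, amount not stated.
- Level checks: at 6 weeks, after a further 6 weeks, and monthly. Table 1 has visits at weeks 4, 6, 8 and 12.
- Conversion: a month taken as 4 weeks, or as 365.25 / 12 / 7 = 4.348 weeks.

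**Reference doses**

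- Loading: 50,000 × 4 = 200,000 IU per 4 weeks.
- Routine step-down: 10,000 × 4 = 40,000 IU per 4 weeks, or 10,000 × 4.348 ≈ 43,482 IU per calendar month.

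**Level ≥60 while on 50,000 IU weekly: what the text permits**

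| Reading | Resulting dose | Ratio to step-down, 4-week month | Ratio to step-down, calendar month |
|---|---|---|---|
| ≥60 rule alone, frequency only | 50,000 IU monthly | 50,000 / 40,000 = 1.25 | 50,000 / 43,482 = 1.15 |
| >35 rule alone | 10,000 IU weekly | 1 | 1 |
| Both rules combined | 10,000 IU monthly | 10,000 / 40,000 = 0.25 | 10,000 / 43,482 = 0.23 |

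Only the first reading inverts the order. On the second, the safety rule adds nothing to the routine one. The first and third differ by 50,000 / 10,000 = 5-fold.

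**Size against loading.** The frequency-only cut leaves 50,000 / 200,000 = 25% of the loading dose, a 75% reduction. The routine step-down leaves 40,000 / 200,000 = 20%, an 80% reduction.

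**When the rules meet**

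- Weeks 6 and 12: a participant on 50,000 IU with a level ≥60 meets both rules at the same measurement, and the result depends on the unstated precedence.
- Week 4, or week 8 after staying on 50,000 IU: if the >35 rule is read as tied to the week 6 and week 12 measurements, only the ≥60 rule applies, and its literal result is 50,000 IU monthly. If the >35 rule applies at any measurement, both rules meet here too.
- Entry requires a level below 25 ng/ml, so reaching 60 by week 4 needs a rise of more than 60 − 25 = 35 ng/ml. Staying on 50,000 IU at week 6 needs ≤35, so reaching 60 at week 8 needs a rise of at least 60 − 35 = 25 ng/ml in two weeks.
- A participant cut to once a month at week 4 reaches week 6 with a level that may still exceed 35. The >35 rule then prescribes weekly dosing until month 6, against the once-monthly instruction. If it prevails, the week 4 inversion lasts about two weeks.

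**Total over 24 weeks (4-week months).** Cut at week 4 and kept at 50,000 IU monthly: 4 × 50,000 + 5 × 50,000 = 450,000 IU. Routine step-down at week 6: 6 × 50,000 + 18 × 10,000 = 480,000 IU. In this comparison the excess is in the monthly rate after the cut and not in the total.

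**Already on 10,000 IU weekly.** The frequency cut gives 10,000 IU monthly, below 40,000 IU per 4 weeks. The order is preserved.

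**The case against.** The strongest reply is that the text supports 10,000 IU once a month at least as well. A participant at 60 has also passed 35 and so qualifies for the 10,000 IU amount. Item 2 of the risk section ties once-monthly dosing to maintenance, a label that section C gives to 10,000 IU. Item 3 says "the dose will be immediately lowered". On that reading there is no inversion. These points stand as a permitted reading, but they do not settle the matter. Section B introduces the 60 ng/mL threshold beside 50,000 units weekly with no smaller step. It also describes maintenance before dialysis as 50,000 units given less often. Keeping the amount and cutting the frequency is therefore not a strained reading.

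It is also fair that the inversion window is narrow. The unit's preliminary mean level was 12.86 ng/ml, and the documents give no response curve for this regimen, so how often a level of 60 would occur during loading is unknown. The conflict at weeks 6 and 12 still needs an answer, whatever its frequency.

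A reader might infer three stronger claims that the documents do not support:

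- That the rules are in the wrong order outright. Two of the three permitted readings do not produce an inversion.
- That the 60 ng/ml rule is the only protection based on 25-OH level. The >35 step-down is itself level-based. Monthly calcium review, with action above 10.5 mg/dl, and an independent medical monitor are separate safeguards.
- That the pilot could not say which regimen it evaluated. Research staff give the doses in the unit, so the doses received can be known, and the ambiguity reaches only participants at 60 or above.

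Nor is the five-fold spread a fault in itself, because a rule that changes frequency naturally depends on the current dose. The fault is that the text does not say which result is meant.

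**Conclusion.** The concern holds in conditional form. The sections state the reduction at about 60 ng/ml in incompatible terms, omit the amount per monthly administration, and do not say which of two overlapping rules governs. For a participant on 50,000 IU weekly, three regimens are permitted. On the frequency-only reading the safety cut leaves 15% (calendar month) to 25% (4-week month) more than the routine step-down.

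That figure assumes that the 50,000 IU amount is kept and that the >35 rule does not also apply. It describes the monthly rate while the cut is in force, which may be short if the >35 rule reapplies at week 6 or 12. Because stated rules on the protocol's main named risk conflict and can give a perverse result, this is more than missing detail and should be corrected. Sample size, power and alpha are unaffected. No view is taken on which dose or rule is right.

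**What to change.** Reconcile section B (Dosing of 25-OH vitamin D in HD Patients), section C (Research Design and Methods; Basic Information, items 1 and 2) and List Possible RISKS (items 2 and 3) into one consistent statement, most simply a table to which the other sections refer. For each 25-OH band and each current dose, it should give the amount per administration, the frequency, and which rule governs when both thresholds are met. It should also say at which measurements each rule is applied, what happens at week 6 or 12 to a participant already moved to once-monthly dosing, and whether the boundary is ≥60 or above 60. The sponsor and medical monitor set the content.

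The cost is one protocol amendment, with no added visits, tests or staff.
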